Neurostimulation & Depression Study

Protocol Summary Document for ProofPilot Remote Studies

ProofPilot Study ID:2518

Principal Investigator

[name]

Study Purpose

Examine the safety and effectiveness of the Fisher Wallace Cranial Electrotherapy Stimulator Device on Major Depressive Disorder using two 20-minute per day treatment sessions over eight weeks.

Study Design

This is a fully remote trial where participants engage at home in the study using the ProofPilot study platform. All potential participant enrollment data, including proof of identity via government ID will be reviewed by licensed medical professionals in the participant's state prior to their full enrollment.

Participants will be randomized into an immediate or delayed treatment arm. The immediate treatment arm participants will be shipped an active Fisher Wallace device limited to Level 2 output even if a participant raises the dial beyond that. The participant will remain with the active device for the full 8 weeks.

In the delayed treatment arm, the participants will receive a sham device that looks exactly the same, but only provides treatment for 2 seconds. At week 4, sham arm participants will be unblinded and shipped an active device (limited to Level 2 output even if a participant raises the dial beyond that). The delayed arm participants will continue with active devices for the remaining 4 weeks of the trial.

Physicians, via a telemedicine visit, will diagnose participants, prescribe the device and provide medical oversight. Participants will self-report adherence and any adverse events on a daily basis through diaries. Self-report outcomes will be collected via online assessments at baseline, 2-week point, 4-week point and 8 week points. In addition, physicians will also conduct an assessment at baseline and week 4.

Weeks 1-4 of this protocol are intended to provide sufficient evidence of safety and effectiveness to support the FDA Premarket approval submission for the Fisher Wallace CES device. Data collected in weeks 5-8 of this protocol, relevant to an ongoing evaluation of safety and effectiveness, may be submitted to FDA in the form of an update report, in accordance with 21 CFR § 814.20(b)(13)(e).

Treatment Instructions

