After receiving a prescription via remote asynchronous telemedicine, the patient is randomized to either an immediate or delayed treatment arm, and delivery of the Fisher Wallace device will be made by UPS/Fedex/UPS. Upon delivery (as identified by shipment tracking code), individuals will be presented with video how-to instructions, and treatment overviews (along with some device usage troubleshooting facts). The device packaging will also include instructions. A PDF version of the instructions, along with FAQs will be made available via ProofPilot for quick reference.

Participants will be directed to use the device twice per day for 20 minutes, once soon after waking up, and the second time per day 20 minutes prior to attempting sleep.

The study timeline will commence upon completion of the first treatment as identified by the participant in ProofPilot.

Participants who have questions about the device will be referred to ProofPilot customer support. All queries will be logged and reported at the end of the study. ProofPilot will refer those questions that can not be answered with an automated frequently asked questions system to PI [name] and/or the manufacturer (Fisher Wallace) for follow-up.

Primary Outcome Measures:

- Change in Beck Depression Inventory Score in “Treatment week 4” versus Baseline in immediate versus delayed arm.

Secondary Outcome Measures:

- Change in Hamilton Depression Rating Scale from Baseline to “Treatment week 4” in immediate versus delayed arm.
- Change in Beck Depression Inventory Score in “Treatment week 2” versus Baseline in immediate versus delayed arm.
- Change in Patient Health Questionnaire - 8 (PHQ-8) score at “Treatment week 4” versus Baseline in immediate versus delayed treatment arm.
- Change in Patient Health Questionnaire - 8 (PHQ-8) score at “Treatment week 2” versus Baseline in immediate versus delayed treatment arm
- Change in Beck Depression Inventory Score from “Treatment Week 4” to “Treatment week 8” in delayed treatment arm (once they have started use of the actual device).
- Device safety, tolerability and adherence over 8 week period as measured by SAFTEE

Sample Size:

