Eligible individuals will then be asked to take a photograph with their mobile device of a government issued ID for identification. They will then enter in shipping information to place an order for the Fisher Wallace Device.

Participants will then complete additional baseline measures including the QIDS-SR, PROMIS Sleep Disturbance, and Jenkins Sleep Scale.

Meanwhile, collected data from PHQ-8, and the Beck Depression Inventory along with proof of identification will be reviewed by medical oversight licensed in the state in which the participant resides and the order released with a prescription for the device. An appointment will be made for the physician to meet with the patient over video telemedicine. During this visit, the physician will evaluate the patient using previously collected baseline data, and their own assessments (MINI, HAM-D) to ensure proper diagnosis and set a professional assessment baseline.

Should the physician feel the participant is a good match, they will issue the prescription for the Fisher Wallace device.

Shipments will be fulfilled by the sponsor's fulfillment capacity by individuals who are not affiliated with the study. All study staff, including remote physicians, will be blinded to who receives the sham and who receives the active device. Tracking information from UPS/Fedex/USPS will trigger tasks based on where the shipment is in the fulfillment process, including at delivery.

At delivery, ProofPilot will automatically trigger instruction tasks, a treatment expectancy survey, and a notification to "Start the trial." The "Start the trial" task will trigger the 2 week, 4 week and 8 week follow up points key to the outcome measures. It will also trigger the window period for the final (week 4) participant/physician video teleconference assessment.

Participants will receive a daily treatment diary at 6:45AM (though they may complete it anytime within an 18 hour period). The daily treatment diary will ask about treatment adherence and any adverse events from the prior day and provide a morning treatment reminder. Participants will also receive an evening

treatment reminder at 7:15PM. Reminders will be presented from ProofPilot in the morning and in the evening adjusted for the participant timezone.

At the end of the study, participants will need to return both the active and sham devices to qualify for compensation.

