- **Promis Sleep Disturbance:** The PROMIS-SD had greater measurement precision than the Pittsburgh Sleep Quality Index (PSQI) and the Epworth Sleepiness Scale (ESS) as indicated by larger test information values across the continuum of severity, despite having fewer total items, a major advantage for both research and clinical settings.³
- **COMBINE SAFTEE** (systematic assessment for treatment of emergent events modified for mental health and substance abuse)

The blue bar indicates shipment/delivery of the active or sham device.

¹ Kroenke, Kurt; Spitzer, Robert L; Williams, Janet B W (2017-05-31). "The PHQ-9". Journal of General Internal Medicine. 16 (9): 606–613. doi:10.1046/j.1525-1497.2001.016009606.x. ISSN 0884-8734. PMC 1495268. PMID 11556941

² Löwe, Burnd; Spitzer; Gräfe; Kroenke; Quenter; Zipfel; Buchholz; Witte; Herzog (February 2004). "Comparative validity of three screening questionnaires for DSM-IV depressive disorders and physicians' diagnoses". Journal of Affective Disorders. 78 (2): 131–140. doi:10.1016/s0165-0327(02)00237-9. PMID 14706723.

³ A. John Rush, Ira H. Bernstein Development of short forms from the PROMISTM sleep disturbance and Sleep-Related Impairment item banks, Behav Sleep Med. 2011 Dec 28; 10(1): 6–24. doi: 10.1080/15402002.2012.636266 PMCID: PMC3261577 NIHMSID: NIHMS335121 PMID: 22250775

	Enroll	Baseline		2-Week	4-Week	8 Week
Inclusion/Exclusion	X					
Consent						
PHQ-8	X			X	X	X
Beck Depression Inventory	X			X	X	X
M.I.N.I Screen	X					
HAM-D	X				X	
Physician Telemedicine Visit	X				X	
Randomization	X					
Treatment Expectancy			X			
Instructions			X			
Quick Inventory of Depressive Symptomatology (QIDS-SR)		X		X	X	X
Jenkins Sleep Scale		X			X	X
Promis Sleep Disturbance		X		X	X	X
COMBINE SAFTEE				X	X	X
Final Feedback & Tolerability						X
Daily treatment adherence and adverse events						

Adverse Event Reporting & Medical Oversight

Licensed medical providers in the state in which the participant lives will provide medical oversight for this effort.

Adverse events will be collected qualitatively via customer support in the ProofPilot platform. In addition, medical oversight staff will automatically receive alerts if participants have a PHQ-8 score over 20 at the 2 week, 4 week or 8 week point. Those participants will also receive notifications to contact local medical support.

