Participants will complete the COMBINE SAFTEE at the 2 week, 4 week and 8 week mark to provide additional data for safety and tolerability not otherwise collected.

All adverse events will be followed up upon and tracked in ProofPilot.

Participant Compensation

Participants may earn up to \$100 for participation in the study.

- \$10 Visa Gift Card for Baseline through completing first Fisher Wallace Treatment (aka 'Start Task') as identified above..
- \$90 presented within 2 weeks of study completion (as defined by return of both the active and shame devices) based on the following:
 - \$20 for each 2 week check in (up to \$60)
 - Up to \$30 as calculated by percentage of daily diaries completed over the 8 weeks

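### The secondary safety and adherence outcome names SAFTEE as its measure, but adherence is recorded in the daily diary and adverse events also reach the trial through the diary and customer support

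*Protocol*

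**What the plan says.** Under Secondary Outcome Measures, the Protocol gives one line for three constructs: "Device safety, tolerability and adherence over 8 week period as measured by SAFTEE". No other instrument is named there.

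Elsewhere it describes the data sources as follows:

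- **Diary.** The opening Study Design section states: "Participants will self-report adherence and any adverse events on a daily basis through diaries". Study Design/Methods repeats this: "The daily treatment diary will ask about treatment adherence and any adverse events from the prior day".
- **SAFTEE.** The list of measures in Study Design/Methods glosses it as "systematic assessment for treatment of emergent events modified for mental health and substance abuse". Adverse Event Reporting & Medical Oversight places it at weeks 2, 4 and 8 and gives its purpose as "to provide additional data for safety and tolerability not otherwise collected".
- **Customer support.** The same section states: "Adverse events will be collected qualitatively via customer support in the ProofPilot platform". Its prose does not mention the diary.
- **Other.** That section also commits to following up and tracking every adverse event in the platform. The schedule table has a separate week-8 item on feedback and tolerability.

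**The concern.** An outcome definition should name the source from which the result will be computed. Here the line names a source that, on the Protocol's own account, does not hold one of the three constructs and holds only part of another. Anyone who follows it literally has no adherence result, and has a safety result drawn from SAFTEE forms only.

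The Study Design section intends weeks 1-4 to supply the safety and effectiveness evidence for the premarket submission. Adherence also matters for interpretation: this is unsupervised home use with a sham comparator, and the number of sessions done is part of what a reader needs in order to judge either a difference or its absence.

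**Working it through.** The Protocol gives no figure for this outcome, so there is none to reproduce. The check is a comparison of sections, with simple counts.

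**1. Which source holds which construct**

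| Construct | Measure named in the outcome | Where the Protocol records it |
|---|---|---|
| Adherence | SAFTEE | Daily diary |
| Adverse events | SAFTEE | Daily diary, customer support, SAFTEE |
| Tolerability | SAFTEE | SAFTEE, plus the week-8 feedback and tolerability item |

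For adherence, the named measure and the recording source do not overlap. For adverse events, the named measure is one of three sources. The Protocol calls it an addition to the others, so the outcome rests on the supplement and leaves out what it supplements.

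**2. Counts per participant**

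Inputs: two sessions a day, a daily diary, eight weeks of treatment, and SAFTEE at weeks 2, 4 and 8.

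- Scheduled sessions through week 4: 2 × 28 = 56. Through week 8: 2 × 56 = 112.
- Diary entries through week 4: up to 28. Through week 8: up to 8 × 7 = 56.
- SAFTEE forms through week 4: 2. Through week 8: 3.

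The 112 assumes that sessions stay scheduled throughout. The delayed arm is shipped its active device at week 4, and the Protocol does not say whether sessions pause while it is in transit.

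**3. Which events the outcome misses as worded**

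An event counts only if it appears on a SAFTEE form. One that appears only in a diary entry or a support record does not. The clearest case is a participant who reports an event in the diary and completes no later SAFTEE; that event is tracked in the platform but is absent from the outcome. For participants who do complete the next form, capture depends on SAFTEE's recall period, which the Protocol does not state. If recall covers the whole interval since the last form, little is missed. If it is shorter, the most exposed interval is the longest one, weeks 4 to 8, when the delayed arm first uses the active device.

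**4. Direction of any bias**

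If every participant who received a device stays in the denominator, adding sources can only leave the event count unchanged or raise it. If only SAFTEE completers are in the denominator, the rate can move either way: it falls if people with events are more likely to miss the form, and it rises if people without events are. The difference between arms can move either way under both denominators. The Protocol gives no event rates or form-completion rates, so no size can be put on it.

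**The case against.** The strongest reply is that this is loose wording in one line. The line does not say that other sources are excluded. The Protocol calls SAFTEE additional, tracks all adverse events whatever their origin, and pays participants partly on diary completion over the eight weeks. How sources are combined, and which denominators are used, is commonly left to a statistical analysis plan, which may exist but is not at hand.

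Much of this stands. A reader might infer that the trial will be unable to report adherence; the documents do not support that, because the diary collects it. A reader might also infer that adverse events in the first two weeks escape the safety outcome. That is not shown either: with recall back to the start of treatment, the week-2 form would capture them for everyone who completes it, and no section says that stopping the device ends follow-up. Nor do the documents support a claim that the active device's event rate would be understated relative to sham, since that depends on dropout patterns they do not give.

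The contradiction itself remains. This is not a detail left for later: the Protocol states a measure, and other sections show it to be the wrong one for adherence and a partial one for safety. An analysis plan that used the diary would be departing from the outcome as the Protocol defines it.

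**Conclusion.** The point holds as a misstated outcome definition. Adherence cannot be derived from the instrument named, and events reported only in the diary or to customer support fall outside the safety outcome as worded. The data exist and are tracked, so nothing is lost if the definition is corrected before analysis.

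The conclusion rests on two readings: that the single instrument named in the line is meant as the measure, and that SAFTEE does not count sessions, which is inferred from the Protocol's description and not from the form itself. The effect on event rates is unquantified. The primary outcome, the planned 175 participants, power and alpha are unaffected. The correction should be made because it is cheap and because the weeks 1-4 safety results are meant for the submission.

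**What to change.** Split the line under Secondary Outcome Measures in two:

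- **Adherence:** sessions reported in the daily diary divided by sessions scheduled, with 56 as the denominator through week 4 and 112 through week 8. State how any days in the delayed arm's device changeover are counted.
- **Safety and tolerability:** participants with any adverse event from the diary, customer support or SAFTEE, among all randomised participants who received a device.

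Compare arms over weeks 1-4, when the contrast is active against sham. Report weeks 5-8 separately, because the delayed arm then uses the active device and a single eight-week count would mix the two exposures. Amend Adverse Event Reporting & Medical Oversight to list the same three sources of adverse events.

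The cost is Protocol wording and the work of matching duplicate reports across sources already collected for the trial. Event rates may look somewhat higher than from SAFTEE by itself. No new data collection is needed.

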Sample size for the study is based on the primary outcome measure of PHQ-8. The difference between the randomized treatment control subjects for the change in score from “Treatment Week 4” versus baseline will be compared with a two-sample t-test at the one-sided 0.025 alpha level. For a planned sample size of 175 total subjects with 1:1 allocation, the study will provide 80% power for an effect size of 0.426 where effect size is based on the ratio of the difference of means over the standard deviation.

p value: two-sample t-test at the one-sided 0.025 alpha level

Statistical Analyses:

Primary analyses of primary and secondary outcome measures will be based on the comparison of the randomized groups via t-tests for means for the change from baseline. Sensitivity analyses for the assumption of normality and for the impact of missing data will be performed. Subgroups results based on sex and race will be provided.

Inclusion/Exclusion

- Age greater than or equal to 21
- US resident
- Can receive packages to their home via UPS/Fedex/USPS
- Major Depressive Disorder
- PHQ-8 Score greater than 10 (show some signs of mild to moderate depression)
- PHQ-8 Score less than 20 (given remote study serious depressed should be excluded)
- Read/write English
- have not contemplated suicide in the past year
- not been institutionalized for mental health issues.
- not currently experiencing problems with alcohol or drug abuse
- can commit to not drinking alcohol 4 hours before bedtime for the duration of the study
- can commit to two (2) 20 minute sessions per day for 8 weeks
- has not used a brain stimulation treatment in one year
- no suspected or known history of heart disease
- no pacemaker
- not under medical supervision for other serious medical condition
- not taking opioids
- are a resident of states in which we have licensed medical professionals
- Any co occurring significant psychiatric disorder that would impair participant's participation
- any use of illicit drugs

Those with a PHQ-8 score greater than 20 will be directed to contact local mental health assistance and will be provided with the National Suicide Prevention Hotline number for immediate assistance.

Recruitment

Individuals in the study will be recruited in two forms targeted to the states in which we have contracted with licensed medical professionals.

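### The protocol names two different primary endpoints: the outcome list says BDI at week 4, the sample-size section says PHQ-8

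*Protocol*

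**What the plan says.** Under Primary Outcome Measures the protocol has a single entry: "Change in Beck Depression Inventory Score in “Treatment week 4” versus Baseline in immediate versus delayed arm". Under Secondary Outcome Measures it lists, among others, "Change in Patient Health Questionnaire - 8 (PHQ-8) score at “Treatment week 4” versus Baseline in immediate versus delayed treatment arm".

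The Sample Size section opens with "Sample size for the study is based on the primary outcome measure of PHQ-8". The next sentence says the week-4 change from baseline "will be compared with a two-sample t-test at the one-sided 0.025 alpha level". The design follows: "For a planned sample size of 175 total subjects with 1:1 allocation", with 80% power at a standardised effect of 0.426 (mean difference divided by standard deviation). A separate line at the end of the section repeats the test and alpha level without naming a scale.

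The Statistical Analyses section says "Primary analyses of primary and secondary outcome measures will be based on the comparison of the randomized groups via t-tests". It names no scale either.

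The Study Design section gives the purpose of the comparison: "Weeks 1-4 of this protocol are intended to provide sufficient evidence of safety and effectiveness to support the FDA Premarket approval submission".

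**The concern.** For the same contrast at the same time point, PHQ-8 is secondary in one section and primary in another, and BDI is the sole primary in the first and absent from the second. Both statements are current text. No section declares co-primary endpoints, a testing order, or which section governs.

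Two things follow. First, it is unclear which scale carries the confirmatory test. Two depression scales measured in the same patients are correlated but not identical, so one can cross the significance threshold when the other does not. If the choice is still open once the results are known, it can be made to suit them. Second, the effect of 0.426 is attached to PHQ-8. If BDI is the primary, the protocol gives no effect assumption for it.

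**Working it through.** **Side-by-side reading**

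| Protocol section | BDI, week-4 change | PHQ-8, week-4 change |
|---|---|---|
| Primary Outcome Measures | primary (only entry) | not listed |
| Secondary Outcome Measures | not listed (week 2 and weeks 4 to 8 are) | secondary |
| Sample Size | not mentioned | called primary |
| Statistical Analyses | no scale named | no scale named |
| Assessment schedule | enrolment, weeks 2, 4, 8 | enrolment, weeks 2, 4, 8 |

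The last two rows do not separate the scales, so the conflict stands.

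**Reproducing the stated power**

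Inputs from the Sample Size section: 175 patients in total allocated 1:1 (87 and 88), one-sided alpha 0.025, standardised effect d = 0.426.

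- Noncentrality = d / √(1/n₁ + 1/n₂) = 0.426 / √(1/87 + 1/88) = 2.818.
- Degrees of freedom = 87 + 88 − 2 = 173; critical t = 1.974.
- Power = P(noncentral t > 1.974) = 80.0%.
- The effect giving exactly 80% power is 0.4259.

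The stated figure reproduces. The calculation is free of scale: it holds for any outcome whose standardised effect is 0.426.

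**Power if BDI is the primary**

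The protocol gives no mean difference or standard deviation for either scale and no effect for BDI. Every effect in this table except 0.426 is therefore an assumption, set on both sides of the design value. The formula and sample size are as above.

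| Assumed BDI effect | Noncentrality | Power |
|---|---|---|
| 0.35 | 2.315 | 63.4% |
| 0.40 | 2.646 | 74.9% |
| 0.426 | 2.818 | 80.0% |
| 0.45 | 2.976 | 84.1% |
| 0.50 | 3.307 | 90.8% |

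**How often the choice of scale changes the result**

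Assume that both scales truly have d = 0.426 and that the two test statistics are bivariate normal, with mean 2.818, unit variance and correlation ρ equal to that of the change scores. Each is compared with 1.974. Then P(exactly one significant) = 2 × [P(one given scale significant) − P(both significant)]. The marginal probability is 0.8006. The protocol gives no correlation, so ρ is assumed.

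| Assumed ρ | P(both) | P(exactly one) | Simulated, 40,000 trials with t-tests |
|---|---|---|---|
| 0.5 | 0.6880 | 0.2252 | 0.227 |
| 0.7 | 0.7137 | 0.1738 | 0.173 |
| 0.9 | 0.7507 | 0.0999 | 0.102 |

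By symmetry, half of each figure is the case where PHQ-8 succeeds and BDI fails: about 11%, 9% and 5%.

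**Type I error if either scale could be claimed**

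If neither scale has an effect and success were claimed on whichever reached one-sided 0.025, the error rate would be 0.05 − P(both significant). That is 0.045, 0.042 and 0.035 for ρ = 0.5, 0.7 and 0.9, against the intended 0.025. The protocol does not propose such a rule; the figures bound what the ambiguity could allow.

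**The case against.** The strongest reply is that the two statements do not weigh the same. The dedicated outcome list is coherent: it uses BDI at week 4, at week 2, and from week 4 to week 8 in the delayed arm, where it is the only depression scale listed. PHQ-8 also serves for eligibility and for safety alerts, and is called primary in one clause only. That clause may be leftover text. This favours BDI as the likely intention, but it remains an inference, and no section says which statement governs. If it is right, the power rationale still rests on a scale that is not the primary.

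A second point is that the closing line of the Sample Size section gives "two-sample t-test at the one-sided 0.025 alpha level" without a scale, so the alpha level could apply equally to BDI. This is fair as to the alpha level. The sample-size basis is still expressly PHQ-8.

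Third, the figures of 10% to 23% depend on assumed correlations and on both scales having exactly the design effect, and they count disagreement in both directions. That is correct. They illustrate what is at stake and do not measure a defect.

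Finally, the document is a protocol summary, and a fuller protocol or SAP may state the primary clearly. That would show the intention, but this text would still contradict itself.

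**Conclusion.** The contradiction is real and unresolved within the protocol, and it must be fixed because it concerns the endpoint that decides a trial meant to support premarket approval. No arithmetic error was found: N = 175 gives 80.0% power at 0.426. Underpowering is not shown either. If BDI is the primary, power is between 63.4% and 90.8% over assumed effects of 0.35 to 0.50, and 80.0% only at 0.426.

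If both scales have a true effect of 0.426 and the change scores correlate at 0.9 to 0.5, the choice of scale alone would alter the conclusion in about 10% to 23% of trials. The severity rests on the regulatory purpose of the week-4 comparison. The illustrative figures show only that the choice can matter.

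**What to change.** Before any week-4 data are compared by arm, name one scale as the single primary in both the outcome list and the Sample Size section.

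- By default, replace PHQ-8 with the Beck Depression Inventory in the Sample Size section, to agree with the outcome list. If the sponsor intended PHQ-8, correct the outcome list instead.
- State that the one-sided 0.025 confirmatory test belongs to that scale only, and keep the other as secondary.
- Confirm that 0.426 is the effect assumed for the chosen scale. If it is not, restate the power at N = 175. Giving the underlying mean difference and standard deviation would help but is optional.

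The cost is wording in two sections, with no extra patients or data. The one drawback is that the restated power will be less favourable than 80% if the assumed effect for the chosen scale is below 0.426; above 0.426 it will be more favourable.

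### The 80% power figure is correct only if all 175 subjects have a week-4 score; no loss is allowed for, and the primary t-test uses neither baseline as a covariate nor week-2 BDI

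*Protocol*

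**What the plan says.** The Sample Size section says that the change to week 4 "will be compared with a two-sample t-test at the one-sided 0.025 alpha level", and continues: "For a planned sample size of 175 total subjects with 1:1 allocation, the study will provide 80% power for an effect size of 0.426". It explains that "effect size is based on the ratio of the difference of means over the standard deviation". No raw difference, standard deviation, loss rate, inflation or separate evaluable number is given.

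The Statistical Analyses section fixes the primary method as "comparison of the randomized groups via t-tests for means for the change from baseline". Missing data appear only in the next sentence: "Sensitivity analyses for the assumption of normality and for the impact of missing data will be performed".

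The Primary Outcome Measures list names the BDI change from baseline to week 4. The schedule of assessments collects the BDI at enrolment and at weeks 2, 4 and 8. The week-2 BDI appears only as a separate secondary outcome.

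**The concern.** Tying 1:1 allocation to the 175 suggests that it is the number randomised. If so, the power claim assumes that nobody is lost before week 4, while the adjacent section provides for missing data.

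The design also leaves room for loss before any follow-up is collected. Under Treatment Instructions, randomisation comes before the device is shipped, and the study clock starts only when the participant reports completing a first treatment. Under Study Design/Methods, that start task triggers the 2-, 4- and 8-week assessments. Someone who is randomised but never starts is not prompted for a week-4 score.

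Two things are at stake. First, weeks 1 to 4 are meant to support a premarket approval submission, so the stated power should describe the analysis that will be done. Second, a t-test on week-4 change among those observed at week 4 takes nothing from people who gave a week-2 score and were then lost. It is unbiased only if loss is unrelated to the change score within each arm.

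**Working it through.** **Inputs from the protocol (Sample Size):** N = 175, 1:1 (87 and 88); one-sided α = 0.025; standardised effect d = 0.426; two-sample t-test; stated power 80%.

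**Inputs assumed:** loss before week 4 of 5%, 10% or 20%, with equal arms among completers. The protocol gives no rate.

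**Formula.** Power = 1 − F(t*; df, δ), where F is the noncentral t distribution function, df = n₁ + n₂ − 2, δ = d / √(1/n₁ + 1/n₂), and t* is the 97.5th percentile of the central t.

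**Step 1: reproduce the stated figure.** With 87 and 88, df = 173, δ = 0.426 / √(1/87 + 1/88) = 2.818 and t* = 1.974. Power is 80.01%. The effect detectable at 80% power is 0.4259, which rounds to the stated 0.426. At 174 analysed (87 and 87), power is 79.8%. So 0.426 is the detectable effect at 175 analysed, with no reserve.

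**Step 2: apply the assumed losses to an unadjusted t-test on completers.**

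| Assumed loss | Analysed | δ at d = 0.426 | Power | Effect detectable at 80% power |
|---|---|---|---|---|
| 0% | 175 | 2.818 | 80.0% | 0.426 |
| 5% | 175 × 0.95 ≈ 166 | 2.744 | 77.9% | 0.437 |
| 10% | 175 × 0.90 ≈ 158 | 2.677 | 75.8% | 0.449 |
| 20% | 175 × 0.80 = 140 | 2.520 | 70.6% | 0.477 |

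**Step 3: what baseline adjustment could recover.** Let r be the correlation between baseline and week 4, and let the baseline SD be k times the week-4 SD. In units of the week-4 variance, a change score has variance 1 + k² − 2rk, and a baseline-adjusted week-4 score has residual variance 1 − r². The ratio of adjusted to change-score variance is

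(1 − r²) / (1 + k² − 2rk).

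The denominator exceeds the numerator by (k − r)², so the ratio is never above 1. Apart from the one degree of freedom spent on the covariate, the powers in Step 2 are therefore conservative for a baseline-adjusted analysis with the same completers.

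The size of the gain depends on r and k, and the protocol gives neither. At an assumed r = 0.5:

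- k = 1: 0.75 / 1.00 = 0.75
- k = 0.7: 0.75 / 0.79 = 0.95
- k = 0.5: 0.75 / 0.75 = 1.00

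The entry limits (PHQ-8 above 10 and below 20) may narrow the baseline spread and so put k below 1. The gain can then be near zero.

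**The case against.** **Nothing stated is miscalculated.** This stands. A reader might infer that the 80% is wrong or that the trial is underpowered. The documents support neither. The figure reproduces, every loss rate above is assumed, and 0.426 is not tied to any stated minimum important difference. If 175 means subjects with week-4 data, the first part of the point reduces to a clarification.

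**A planned sensitivity analysis is a routine precaution, not a forecast of loss.** This is fair. The protocol also has retention measures: twice-daily reminders, and payment linked to check-ins and diaries. They make loss less likely but do not replace an allowance for it.

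**Handling of missing scores belongs in the SAP, which is not shown.** This stands in part. A reader might infer that the protocol commits to a complete-case analysis. It does not say so; that is an inference from a t-test on week-4 change, with no imputation stated and missing data left to sensitivity analyses. An SAP could specify imputation, and the sensitivity analyses could use the week-2 BDI. However, the protocol itself names an unadjusted t-test as primary and states the power without qualification, so both are open to comment.

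**A t-test on change is a valid prespecified analysis.** This is true. The case for the model is that it uses data already collected, at almost no cost, and needs a weaker assumption about loss.

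**Completer t-test figures do not describe a repeated-measures model.** This is correct. The restated power must be for whichever analysis becomes primary.

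**Conclusion.** The point holds as a recommended improvement, not as an arithmetic error. The 80% at 0.426 is right for 175 analysed subjects and leaves no reserve. If 175 is the number randomised and an unadjusted t-test is run on completers, power is 77.9%, 75.8% and 70.6% at assumed losses of 5%, 10% and 20%. At 10% loss the detectable effect moves by 0.449 − 0.426 = 0.023 SD, and at 20% by 0.477 − 0.426 = 0.051 SD.

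It is tempting to say that baseline adjustment would make good a loss of about 25%. The documents do not support that: it needs r = 0.5 and equal SDs at baseline and week 4, and Step 3 shows the gain vanishing at k = 0.5.

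One related inconsistency affects any restatement. The power statement opens with "Sample size for the study is based on the primary outcome measure of PHQ-8", while the listed primary outcome is the BDI. Because the effect is standardised, the arithmetic above does not change, but no BDI difference or SD is given in support of 0.426.

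**What to change.** 1. In Sample Size, state whether 175 is the number randomised or the number with week-4 data. If it is the number randomised, give the expected loss and restate the power or the detectable effect for the analysis that will be primary. The Step 2 figures apply to the unadjusted t-test and serve as conservative values for a baseline-adjusted model. No added enrolment is asked for.

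2. In Statistical Analyses, make the primary analysis a repeated-measures model of BDI at weeks 2 and 4, in all randomised participants with a post-baseline score. Use baseline BDI as covariate and the week-4 treatment contrast as the test. Keep the t-test on change as a sensitivity analysis. The model brings in people seen at week 2 and lost before week 4. It does not recover those with no post-baseline score, so the loss allowance in item 1 is still needed.

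The cost is wording, slightly more analysis work and a slightly less favourable stated power. Visits, procedures and the number of participants do not change.
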